Study Protocol Title:

Elevation of the Fetal Buttocks Prior to External Cephalic Version

Study Sponsor:

AdventHealth Orlando

Principal Investigator:

Principal investigator: D. [name].

NCT04538261

IRB Approval Date:

11/23/2021

List of Abbreviations:

ECV	External Cephalic Version
FHR	Fetal heart rate
FDA	Food and Drug Administration
VAS	Visual Analog Scale
EMR	Electronic medical record

Introduction

This document is a protocol for a human research study. This study will be conducted in accordance with applicable federal regulations and institutional research policies and procedures.

Background Information and Scientific Rationale

Breech presentation, where the baby's buttocks or feet are presenting first, occurs in 3-4% of pregnancies after 37 weeks gestational age.¹ Options for patient with a term breech baby include cesarean delivery, attempted vaginal breech delivery, or attempted conversion from breech to a head first (cephalic) presentation using a procedure called external cephalic version (ECV). Breech vaginal deliveries are increasingly less common due to findings from a meta-analysis and systematic review that a planned cesarean delivery reduced both perinatal and neonatal death.

Many patients would like the opportunity to deliver vaginally, and in most cases those patients with a breech presentation after 36 weeks gestational age may be offered an ECV. ECV has varying rates of success depending on many factors, including whether the woman has had any prior pregnancies, the position of the baby, the amount of amniotic fluid, and whether the buttocks are deeply engaged in the pelvis.

Many obstetricians prefer to attempt ECV between 36-37 weeks gestational age because the success rate is similar to 34 weeks, but the baby is less likely to need neonatal intensive care if an emergent cesarean delivery is necessary. The success rate for nulliparous patients (those who have never delivered before) without spinal or epidural anesthesia is approximately 30%.

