There are very few interventions to improve the success of ECV. A randomized trial of nulliparous patients undergoing ECV with and without spinal anesthesia found a success rate of 32% without and 67% with anesthesia. While this is an impressive improvement in success, many of our patients do not wish to have regional anesthesia. Regional anesthesia also increases the length of stay and cost of the ECV procedure. One potential method of improving ECV success is to elevate the fetal buttocks during the procedure, although this has been poorly studied. One group reported that they had zero successful ECV procedures when the buttocks were lower than -1 station, versus a 66% success if the buttocks were at or higher than -3 station.

The Safe Obstetric Systems Inc. Fetal Pillow is a balloon device approved by the United States Food and Drug Administration (FDA) for elevating the fetal head during cesarean deliveries performed during the 2nd stage, after the patient has been pushing. The device is placed into the vagina, filled with sterile saline, and inflated to push the head up and out of the pelvis. Using the device to elevate the fetal buttocks prior to an ECV is an off-label usage of the product. Although unlikely, it is possible that the Fetal Pillow may decrease ECV success rates or cause unforeseen harm to the mother or fetus.

The objective of this research project is to assess the efficacy of the Fetal Pillow during ECV procedures for nulliparous women without regional anesthesia.

Study Objectives

Primary Objective

The primary objective of this study is to evaluate the successful conversion of a breech to vertex presentation. Successful conversion will be confirmed via ultrasound immediately following the ECV procedure.

Secondary Outcomes

Maternal outcomes:

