1. MRN
2. Age
3. Weight
4. Height
5. Body mass index
6. Ethnicity
7. Gravidity (total number of pregnancies including this one)
8. Parity (births > 20 weeks)
9. Number of vaginal deliveries
10. Number of cesarean deliveries
11. Measurement of inferior aspect of rib to pubic symphysis
12. Date and time of delivery
13. Induction
14. Presence of vaginal delivery (SVD or OVD)
15. Presence of vacuum assisted delivery
16. Presence of forceps assisted delivery
17. Presence of cesarean delivery
18. Fetal presentation at time of delivery
19. Presence of postpartum hemorrhage (> 1,000 mL of measured blood loss)
20. Presence of placental abruption
21. Presence of shoulder dystocia
22. Date and time of discharge after delivery
23. Length of stay
24. Cost of hospital stay (labor and delivery)
25. Patient zip code
26. Patient insurance

Neonatal outcomes:

1. Presence of stillbirth
 - a. If stillbirth, estimated gestational age this occurred (weeks and days)
2. Birthweight (grams)
3. Apgar score at 1 minute
4. Apgar score at 5 minutes

5. Presence of neonatal intensive care unit admission
6. Presence of intubation
7. Presence of neonatal humeral fracture
8. Presence of neonatal clavicle fracture
9. Presence of neonatal skull fracture
10. Neonatal length of stay
11. Cost of neonatal stay

Procedural Outcomes

1. Date of procedure
2. Time of procedure

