3. EGA
4. Name of obstetrician performing ECV procedure
5. Presence of inflated Fetal Pillow
6. Presence of terbutaline
7. Presence of palpable fetal head
8. Estimated fetal weight (kg)
9. Fetal head position *confirmed by ultrasound
10. Fetal back position
11. Position of fetal neck
12. Location of placenta
13. Amniotic fluid index (4 quadrant total)
14. Fetal station (-3 through +3)
15. Maternal cervical dilation (cm)
16. Presence of rupture of membranes within 1 hour of procedure
17. Presence of 3 or more contractions in 10 minutes immediately prior to procedure
18. Bleeding equal to a menstrual period during or within 1 hour of the ECV procedure.
19. Development of a pelvic hematoma during or within 1 hour after the ECV procedure.
20. Development of a vaginal laceration during insertion of the device, the ECV procedure, or removal of the device.
21. Presence of fetal bradycardia
22. Presence of fetal heart rate decelerations
23. Presence of delivery within 1 hour of procedure
24. VAS pain score immediately prior to ECV (-3 minutes)
25. VAS pain score immediately after insertion of Fetal Pillow (+ 2 minutes)
26. VAS pain score after inflation/sham inflation (+ 1 minute)
27. VAS pain score immediately after each ECV procedure attempt, maximum of 4 attempts (+ 2 minutes)
28. Total number of attempts
29. Procedure successful Y N (Primary Outcome) *confirmed by ultrasound
30. Fetal head position post ECV *confirmed by ultrasound
31. Number of forward rolls
32. Number of reverse rolls
33. Note which procedure was successful

34. Did patient request to have spinal or epidural anesthesia after initiation of ECV procedure (off of study protocol): Y N
35. Presence of regional anesthesia prior to ECV procedure (Excluded from study)
36. Length of time from start of procedure to hospital discharge
37. Cost of hospital stay for ECV procedure

Study Design

Research Design

This is a prospective, randomized double-blind clinical trial evaluating the effect of a balloon device to elevate the fetal buttocks during external cephalic version procedures. Eligible study population: pregnant women between 37-40 weeks estimated gestational age with a breech presenting baby and no contraindications to ECV.

Study Agent, Device, and/or Intervention Description:

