Clinical trial monitoring is conducted to ensure that the rights and well-being of trial participants are protected. Reported trial data are accurate, complete and verifiable.

Clinical trial monitoring will be conducted by AdventHealth Office of Research Integrity monitoring team to ensure compliance with all applicable federal and state regulations, ICH GCP E6 (R2) standards and approved protocol. This study will be monitored using a risk-based approach. A monitoring plan will be created to ensure patient safety, data quality and integrity is ongoing throughout the life of the study. The frequency and elements of monitoring will be outlined in the monitoring plan. The monitor will ensure study is conducted, recorded and reported as required by federal regulations and IRB of record. Monitoring will be conducted on-site and/or remote. After completion of site monitoring, a report will be provided to PI and study team. The PI and study team are required to review the report and work on significant findings or discrepancies to resolution. If any findings are required to be reported to the IRB, the PI will be made aware and prompted to self-report. All serious and continuing non-compliance is shared with the Research Oversight Committee who may require appropriate actions.

Protocol Deviations

All deviations and SAEs must be reported promptly to AH ORI and regulatory team. SAEs must be reported within 24 hours of discovery. Any SAE required to be reported to the FDA and IRB will be completed with the assistance of the central regulatory team in conjunction with the principal investigator and study team.”

Data Sharing (outside of AdventHealth Orlando): N/A

Sample Size Determination

Based on prior studies of patients without regional anesthesia who had a success rate of approximately 49%, and assuming a 1:1 allocation of intervention and control subjects, with an 80% power, and a 2-sided 5% significance level, we calculated a sample of size of 69 in each group to increase the success rate from 49% to 73.5%. Assuming a 10% case dropout rate we will enroll 76 patients in each arm (152 total participants).

Statistical Analysis Plan

Primary Objective Analysis

The success of ECV procedures for the intervention group compared to the control group will be analyzed using chi-square and Fisher exact tests. A P value of <0.05 will be considered statistically significant.

Secondary Objective Analysis

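### The primary comparison is unadjusted although the protocol names and collects parity and station: a modest, unquantified loss of precision, with two tests listed and none named as deciding

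*Combined protocol and SAP*

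**What the plan says.** Under Statistical Analysis Plan, Primary Objective Analysis, the method is a single sentence: "The success of ECV procedures for the intervention group compared to the control group will be analyzed using chi-square and Fisher exact tests", with significance at P below 0.05. It does not say which test decides, when each applies, or whether the chi-square is continuity-corrected. It names no covariate. The Randomization section describes a 1:1 block scheme and names no stratification factor.

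The Background describes baseline differences in prognosis. It says that "ECV has varying rates of success depending on many factors, including whether the woman has had any prior pregnancies" and adds "whether the buttocks are deeply engaged in the pelvis". It also cites one group with no successes "when the buttocks were lower than -1 station, versus a 66% success if the buttocks were at or higher than -3 station". Parity is on the list of maternal outcomes and fetal station on the list of procedural outcomes.

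Two statements bear on whether parity will vary. The stated objective is "to assess the efficacy of the Fetal Pillow during ECV procedures for nulliparous women without regional anesthesia". Research Design gives "Eligible study population: pregnant women between 37-40 weeks estimated gestational age with a breech presenting baby and no contraindications to ECV", and neither the inclusion nor the exclusion list mentions parity.

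On pain, Visit 1 takes a 100 mm VAS score from every woman before the procedure and further scores afterwards. Secondary Objective Analysis offers only unadjusted tests, and for maternal and neonatal outcomes. VAS is listed under Procedural Outcomes, so the text does not clearly assign it a test at all.

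**The concern.** When a protocol itself says that two baseline features drive the outcome and records both for every woman, leaving them out of the primary analysis gives up precision that needs no new measurement and no extra patients.

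Listing two tests for one 2x2 table adds a smaller problem. If the chi-square is uncorrected, some results will be significant by one test and not by the other, and the plan gives no rule for that case. The choice would then be open after the data are seen. Visit 2 says that investigators are unblinded after each procedure, and the Safety Monitoring Plan reviews interim outcome data after 10 subjects and every 20 thereafter, so the rule is best fixed early.

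**Working it through.** **1. The plan's own sample size.** Inputs from Sample Size Determination: 49% versus 73.5%, 1:1, 80% power, two-sided 5% ("we calculated a sample of size of 69 in each group to increase the success rate from 49% to 73.5" per cent).
- Mean rate 0.6125, difference 0.245.
- Uncorrected: n = [1.96 x sqrt(2 x 0.6125 x 0.3875) + 0.8416 x sqrt(0.49 x 0.51 + 0.735 x 0.265)]^2 / 0.245^2 = (1.3504 + 0.5612)^2 / 0.0600 = 60.9.
- Continuity-corrected: (60.9/4) x [1 + sqrt(1 + 4/(60.9 x 0.245))]^2 = 15.22 x (2.126)^2 = 68.8, that is 69.

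So the stated 69 matches the continuity-corrected formula. The sizing points to a conservative test; the analysis text does not say so.

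**2. Exact behaviour of each test.** All 70 x 70 outcomes at 69 per arm were enumerated under two independent binomials.

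| True rates | Uncorrected chi-square | Yates | Fisher | Uncorrected/Fisher split |
|---|---|---|---|---|
| 49% vs 73.5% | 84.4% | 79.9% | 79.9% | 4.4% |
| 49% vs 49% | 4.98% | 3.29% | 3.29% | 1.7% |
| 49% vs 70% | 70.9% | 64.8% | 64.8% | 6.1% |
| 49% vs 65% | 47.2% | 40.4% | 40.4% | 6.8% |

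In every split the chi-square is significant and Fisher is not, so rejecting on either test has the size of the uncorrected chi-square: 4.98% at 49%, and 4.7-5.1% over the common rates tried from 30% to 73.5%. Yates and Fisher split in 0.003% of trials at the design rates. Example: 34/69 versus 46/69 gives P = 0.039 uncorrected, 0.058 Yates and 0.057 Fisher.

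**3. Gain from adjustment.** The documents give no parity mix, parous success rate or station mix, so everything here is assumed. Overall rates were held at 49% and 73.5%, with one odds ratio for the device in all women. The adjusted test is a Firth-penalized logistic model with arm, parity and one binary station term, tested by likelihood ratio (20,000 simulated trials per scenario; 20-50% nulliparous, 15-25% at low station). Crude power is 84.4%.

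| Odds ratio of each covariate | Adjusted power | Gain (points) |
|---|---|---|
| 1 (not prognostic) | 84.1-84.4% | about 0 |
| 2 | 85.3-86.0% | 0.9-1.6 |
| 3 | 87.0-87.9% | 2.6-3.5 |

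A separate simulation with two covariates at 50% prevalence and ordinary logistic regression gave 84.4% crude and 86.6% adjusted at odds ratios of 2 (gain 2.2), and 84.8% and 89.2% at 3 (gain 4.4). If only nulliparous women enrol, parity contributes nothing.

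**4. A very strong station effect.** Suppose 25% are at low station with 2% control success. High-station control success is then (0.49 - 0.25 x 0.02)/0.75 = 64.7%. A common odds ratio of 7.78 is needed to reach 73.5% overall; it gives 14% at low station and 93% at high station (0.25 x 0.137 + 0.75 x 0.934 = 0.735). Adjusted power is then 98%. If instead the device brings both strata to 73.5%, adjusted power is 87%. Over 15-25% at low station and 2-30% low-station control success, a station-stratified test has 85-98% power under the common odds ratio and 84-87% under equalised success, a gain of about 0-2 points in the second case.

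**5. Pain score.** With 69 per arm, a t-test has 80% power at a standardized difference of 0.48. ANCOVA divides this by sqrt(1 - r^2), where r is the assumed correlation with the pre-procedure score. At r = 0.3: 0.480/0.954 = 0.504, power 84%. At r = 0.5: 0.480/0.866 = 0.555, power 90%.

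**The case against.** The strongest reply is that nothing falls short of what the plan promises. It asks for 80% power, every reading gives about 79.9% or more, and the 69 per arm already allows for a conservative test. On the reading that fits the sample size, the two listed tests almost never disagree. This stands. A reader might infer that the primary test is biased, that two tests inflate the error rate, or that the trial is underpowered because of this choice. The figures above support none of these. The 4.4-point gap between Fisher and uncorrected chi-square is measured against a power that the plan never claimed.

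A second reply is that the cited contrast in success by station (none against 66%) invites an expectation of large gains, and that this is not safe. It also stands. Gains to well above 90% need the device's odds ratio to be the same at every station. The device is meant to raise the buttocks, so its benefit could well be greater where they are low, and the gain then shrinks to about 0-2 points.

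A third reply is that Fisher is meant only for small cells. The plan does not say so. At the design rates the smallest expected count is 69 x 0.3875 = 26.7, so that rule would give Fisher no part in the primary test.

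Finally, adjustment needs a station coding chosen in advance, and station has no stated time of recording. It is listed beside cervical dilation, which is examined before insertion, so a pre-insertion value is the likely reading. This is a reason to write it down; it does not show that station is measured too late.

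**Conclusion.** The concern holds as a minor point about precision and pre-specification. The unadjusted comparison is valid and adequately powered at the design rates. What is unused is baseline information that the protocol itself calls prognostic. The gain from using it is an assumption: about none if the covariates do not predict success, roughly 1-2 points at odds ratios near 2 and 3-4 points at 3. It is larger only with a strong station effect and a constant device odds ratio. Parity helps only if parous women enrol, which the objective and the eligibility criteria leave unresolved.

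The ambiguity over the test matters only if the chi-square is uncorrected. A reader might take 4.4% as the most that can go wrong; it is the figure at the design rates, and the split is 1.7% under the null and 6.8% at 49% versus 65%.

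The gain for the pain score rests on assumed correlations and on normal theory.

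**What to change.** Before any comparison by arm:

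- **Name one deciding primary analysis.** An example is a Firth-penalized logistic regression of success on arm, one station term and parity, with the two-sided 5% penalized likelihood-ratio test of arm deciding and a standardized risk difference with 95% CI reported. Its simulated size was 4.6-5.3% over the 62 scenarios run. Penalization should apply whatever the data show: with 2% low-station success, ordinary logistic regression had no finite estimate in 8-36% of simulated trials at the planned effect.
- **Reconcile the nulliparous objective with the eligibility criteria.** Include parity only if it then varies.
- **State on the data form that station is recorded before device insertion, and fix its coding.** The Background gives no rate between its two station groups and so supplies no binary cut; a linear score of the recorded -3 to +3 needs none.
- **Keep the uncorrected chi-square as a sensitivity analysis that cannot overturn the primary result**, and drop Fisher as a second primary test. The adjusted and crude verdicts differed in 2-9% of simulated trials at covariate odds ratios of 1-5, so the order of precedence must be written down.
- **If no adjustment is wanted**, name one test and state its continuity correction. That alone removes the split.
- **Separately**, name the post-procedure VAS score to be compared and analyse it by ANCOVA on the pre-procedure score.

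The cost is SAP wording, one timing note on the form and slightly more analysis work. The model should stay small (arm plus at most two terms), and its size should be re-checked by simulation if the coding changes.

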Maternal and neonatal outcomes will be analyzed using chi-square and Fisher exact tests for categorical variables, unpaired t-tests for continuous variable, and non-parametric tests for continuous variables that are not normally distributed. P values <0.05 will be considered statistically significant.

Potential Risks and Benefits

Potential Benefits

The Fetal Pillow device may improve the ECV success rate.

Potential Risks

Although unlikely based on prior device usage during 2nd stage arrest, it is possible the device may cause vaginal bleeding, increased pain during the procedure, or either no change in success or a lower success rate compared to performing the procedure without the device. Terbutaline administration may cause maternal tachycardia, irritability, chest pressure or chest pain. While loss of confidentiality is a potential risk to patients, patient information will be de-identified prior to analysis and only study personnel will have access to patient information. The United States Food and Drug Administration has determined that this study protocol is a nonsignificant risk (NSR) study (Review # Q191927, notification received December 18, 2019).

Mitigation of Risks

Patients will be asked prior to administration of terbutaline if they have contraindications, which is standard practice prior to using this medication.

Provisions to Protect the Privacy Interest of Subjects

The steps to protect the privacy of subjects have been described previously. Briefly, study documentation and patient information will be stored in a separate file on a password-protected laptop stored in a locked office. Drs. [name], [name] and research team will have access to both files.

Early Withdrawal of Subjects

Investigator Withdrawal of Subjects.

Inability to place Fetal Pillow: If the Fetal Pillow cannot be placed, for example due to pain, or the Fetal Pillow cannot be inflated, the patient will be withdrawn from the study. However, she may undergo an attempted ECV outside of the study protocol if she wishes.

Delivery at a hospital outside of the AdventHealth Orlando system: If the patient delivers outside of the AdventHealth Orlando system she will be withdrawn from the study analysis.

Subject Request for Withdrawal from Study

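### Harms get P<0.05 tests or no stated analysis: no risk difference or confidence interval is planned, and the choice between Fisher and chi-square is left open

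*Combined protocol and SAP*

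**What the plan says.** The Secondary Objective Analysis has two sentences. The first gives the tests: "Maternal and neonatal outcomes will be analyzed using chi-square and Fisher exact tests for categorical variables", with t-tests or non-parametric tests for continuous variables. The second gives the threshold: "P values <0.05 will be considered statistically significant". No rule separates the two categorical tests, no continuity correction is mentioned, and no effect estimate or interval is planned.

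The harms sit in three lists under Secondary Outcomes:

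- **Maternal outcomes, items 19-21:** postpartum hemorrhage, abruption ("Presence of placental abruption") and shoulder dystocia.
- **Neonatal outcomes, items 1 and 5-9:** stillbirth, intensive care admission, intubation and three kinds of fracture.
- **Procedural Outcomes, items 16 and 18-23:** membrane rupture, bleeding, pelvic hematoma, laceration ("Development of a vaginal laceration during insertion of the device, the ECV procedure, or removal of the device"), bradycardia, decelerations and delivery within an hour.

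The analysis sentence names the first two groups and not the third. The Background section accepts that this off-label use could "cause unforeseen harm to the mother or fetus".

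**The concern.** A test at 5% answers whether the arms differ detectably. For a rare harm in a trial sized on a common efficacy outcome, the useful question is how large an excess risk the data still allow. Only an estimate with an interval answers that, and none is planned.

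Two further gaps add to this. The verdict on a sparse table can change with the test, and the test can be chosen after the data are seen. And the harms most plausibly linked to the device are in the list that the analysis sentence leaves out. If they are meant to be covered, they get only a P value. If not, they have no stated between-arm analysis.

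At stake is what the trial can say about the safety of inflating the device in this setting.

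**Working it through.** **Inputs.** Sample Size Determination gives 49% v 73.5%, "a 2-sided 5% significance level", "with an 80% power", and "assuming a 1:1 allocation of intervention and control subjects", leading to 69 per arm, or 76 enrolled per arm. I take tests as two-sided, as there; the secondary section does not say. The documents give no expected harm rate, so every harm rate and event count below is an assumption.

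**1. The plan's own figure.** With Δ = 0.245 and mean rate 0.6125:

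n₀ = [1.960·√(2·0.6125·0.3875) + 0.8416·√(0.49·0.51 + 0.735·0.265)]² / 0.245² = 60.9, so 61 per arm.

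With continuity correction, n = (n₀/4)·[1 + √(1 + 4/(n₀Δ))]² = 68.8, so 69 per arm, which matches. Also 69 × 1.10 = 75.9, so 76. The size was set for the primary outcome alone.

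**2. k events against 0, by test.** Two-sided Fisher P = 2·C(n,k)/C(2n,k). Uncorrected chi-square = 2nk/(2n−k); for k = 5 and n = 76 this is 760/147 = 5.17.

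| k v 0, n = 76 per arm | Fisher | Yates chi-square | Uncorrected chi-square |
|---|---|---|---|
| 3 | 0.245 | 0.244 | 0.080 |
| 4 | 0.120 | 0.129 | 0.043 |
| 5 | 0.058 | 0.069 | 0.023 |
| 6 | 0.028 | 0.037 | 0.012 |

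At 69 per arm, 5 v 0 gives 0.058, 0.068 and 0.023. Fisher needs 6 v 0 to reach 5%; uncorrected chi-square needs 4 v 0. With one control event at 76 per arm, Fisher gives 0.063 for 7 and 0.034 for 8.

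**3. Power.** For 1% v 5%, sum Bin(i; n, 0.01)·Bin(j; n, 0.05) over all tables with P<0.05. For a control rate of 0, take the chance of at least 6 events (Fisher) or at least 4 (uncorrected chi-square).

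| Assumed rates, sham v inflated | Fisher, n=69 | Fisher, n=76 | Chi-square, n=69 | Chi-square, n=76 |
|---|---|---|---|---|
| 1% v 5% | 7.3% | 9.7% | 25% | 28% |
| 0 v 5% | 13% | 18% | 45.5% | 53% |
| 0 v 10% | 70% | 78% | 92% | 95% |

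**4. What an interval would show.** The Newcombe interval combines the Wilson limits of the two arms. For 5/76 v 0/76 the Wilson limits are 2.84% to 14.49% and 0 to 4.81%. The difference is 6.58 points. The lower limit is 6.58 − √[(6.58−2.84)² + 4.81²] = 0.5 and the upper is 14.5. For 5/69 v 0/69 it is 7.2 points, 0.6 to 15.9.

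For 3/76 v 0/76, non-significant by all three tests, the Wilson limits of 3/76 are 1.35% to 10.97%. The difference is 3.95 points, the lower limit 3.95 − √[(3.95−1.35)² + 4.81²] = −1.5, and the upper limit 11.0.

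**5. No events in an arm.** The exact two-sided 95% upper limit is 1 − 0.025^(1/n): 4.7% for 0/76 and 5.2% for 0/69.

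**The case against.** Several points on the other side stand.

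- **5 v 0 is not simply non-significant under the plan.** A reader might infer that it is. Fisher gives 0.058, and Fisher is the usual choice with expected counts of 2.5 per arm. But the plan also names chi-square, which uncorrected gives 0.023. The Newcombe interval for this table excludes zero too, so its non-significance reflects Fisher's conservatism. The supportable complaint is the open choice of test.
- **The plan does not say that a non-significant harm will be reported as no safety difference.** A reader might expect such a report, but no section says so, and nothing prevents the counts being shown.
- **Harms are not judged by P values alone.** Adverse Event Reporting grades events by severity and relatedness, and the Safety Monitoring Plan has a review after 10 randomized women and every 20 thereafter. Neither uses a P value. They are oversight during the trial, however, and supply no between-arm estimate for the final report.
- **The comparison isolates inflation.** Under Visit 1, the device is inserted in every woman. Injuries from insertion or removal can occur in both arms, and no between-arm analysis, with or without an interval, will reveal a risk that the arms share.

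It can also be said that procedural harms fall under the general Secondary Outcomes heading and so under the same rule. That is a fair reading, but the analysis sentence does not state it, and on that reading they still get no interval.

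**Conclusion.** The concern holds as a gap in the analysis plan. Categorical maternal and neonatal harms get only a 5% test, procedural harms get no named analysis, and no harm gets a risk difference or interval. The unstated choice of test decides tables such as 4 v 0 and 5 v 0.

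The size rests on assumed rates. For 1% v 5%, power is at most 28% by either test at the planned sizes. At 0 v 10% it is 70% or more, so the weakness concerns rare harms and moderate excesses rather than very large ones. Whichever test is used, 3 v 0 at 76 per arm is non-significant while an excess of up to 11.0 points remains compatible with the data. The conclusions are the same at 69 and 76 per arm.

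The documents do not support the stronger claim that the trial would declare the device safe.

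**What to change.** In the Secondary Objective Analysis, for maternal items 19-21, neonatal items 1 and 5-9, and procedural items 16 and 18-23:

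1. Replace the P<0.05 rule with the count and percentage by arm and the risk difference (inflated minus sham) with a Newcombe 95% confidence interval. Name the method, since sparse tables are sensitive to it.
2. Where an arm has no event, give the exact two-sided 95% upper limit.
3. State that a non-significant harm comparison will not be interpreted as evidence of safety.
4. Report insertion and removal injuries pooled over both arms with an exact interval. Item 20 records laceration at insertion, version or removal as one item, so the pooled figure covers all three unless the form separates them.

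I would not add a composite of the procedural items. It would pool injuries with ungraded decelerations and delivery within an hour, which could dominate the count.

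The cost is SAP wording and one extra table, with no more women to enroll. The downside is a visibly less reassuring safety statement.
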